#### 5.1.2.2 Concomitant treatment start date imputation

The following table explains the notation used in the logic matrix. Please note that **missing start dates** will not be imputed.

	Day	Month	Year
Partial CMD Start Date	Not used	MON	YYYY
Treatment Start Date	Not used	TRTM	TRTY

The following matrix explains the logic behind the imputation.

	MON MISSING	MON < TRTM	MON = TRTM	MON > TRTM
YYYY	(1)	(1)	(1)	(1)
MISSING	Uncertain	Uncertain	Uncertain	Uncertain
YYYY < TRTY	( 2.a )	( 2.b )	( 2.b )	( 2.b )
	Before Treatment Start	Before Treatment Start	Before Treatment Start	Before Treatment Start
YYYY = TRTY	( 4.a )	( 4.b )	( 4.a )	( 4.c )
	Uncertain	Before Treatment Start	Uncertain	After Treatment Start
YYYY > TRTY	( 3.a )	( 3.b )	( 3.b )	( 3.b )
	After Treatment Start	After Treatment Start	After Treatment Start	After Treatment Start

- 1. If the CM start date year value is missing, the imputed CM start date is set to one day prior to treatment start date.
- 2. If the CM start date year value is less than the treatment start date year value, the CM started before treatment. Therefore:
  - a. If the CM month is missing, the imputed CM start date is set to the mid-year point (01JulYYYY).
  - b. Else if the CM month is not missing, the imputed CM start date is set to the midmonth point (15MONYYYY).
- 3. If the CM start date year value is greater than the treatment start date year value, the CM started after treatment. Therefore:
  - a. If the CM month is missing, the imputed CM start date is set to the year start point (01JanYYYY).
  - b. Else if the CM month is not missing, the imputed CM start date is set to the month start point (01MONYYYY).
- 4. If the CM start date year value is equal to the treatment start date year value:
  - a. And the CM month is missing, or the CM month is equal to the treatment start date month, then the imputed CM start date is set to one day prior treatment start date.
  - b. Else if the CM month is less than the treatment start date month, the imputed CM start date is set to the mid-month point (15MONYYY).
  - c. Else if the CM month is greater than the treatment start date month, the imputed CM start date is set to the month start point (01MONYYYY).

If complete (imputed) CM end date is available and the imputed CM start date is greater than the (imputed) CM end date, then imputed CM start date should be set to the (imputed) CM end date.

#### 5.2 Statistical models

#### 5.2.1 Primary analysis

The following MMRM model will be used for the primay estimand and supplementary estimand.

```
change from baseline in SANDE = intercept + baseline SANDE + treatment + day + Sjogren's Syndrome (yes/no) + treatment*day + baseline SANDE * day + error
```

change from baseline in corneal fluorescein staining score = intercept + baseline corneal fluorescein staining score + treatment + visit + Sjogren's Syndrome (yes/no) + treatment\*visit + baseline corneal fluorescein staining score \* visit + error

The SAS Proc MIXED will be used to perform the MMRM analyses. The data structure is one record per subject per analysis visit. SAS codes for all statistical methodology described in this section, including the imputation implementation, will be included as programming note in TFL Shells.

The following SAS code can be used to perform the primary analyses:

RUN;

#### Where

<Dataset> = dataset to store SANDE score or corneal fluorescein staining score where the structure is one record per FAS subject per day/visit.

<Chg> = change from baseline in SANDE score or corneal fluorescein staining score

<Treatment> = randomized treatment assignment

< Sjogren's Syndrome> = diagnosis of Sjogren's Syndrome at baseline

<Visit> = ordered day or visit

Novartis	For business use only	Page 32
SAP		CECF843A2201

<Baseline> = baseline value for SANDE score or corneal fluorescein staining score

The terms in the brackets are to be adjusted according to the real data set and variable names. If an MMRM model (for corneal fluorescein staining score) with unstructured covariance matrix does not converge, choose the covariance structures in the following order until convergence is reached:

- Toeplitz: change to TYPE = TOEP in the 'Repeated' statement;
- First-order autoregressive: change to TYPE = AR(1) in the 'Repeated' statement;
- Compound symmetry: change to TYPE = CS in the 'Repeated' statement.

If an MMRM model (for SANDE score) with Toeplitz covariance matrix does not converge, choose the covariance structures in the following order until convergence is reached:

- First-order autoregressive: change to TYPE = AR(1) in the 'Repeated' statement;
- Compound symmetry: change to TYPE = CS in the 'Repeated' statement.

P-values from three comparisons requested in Section 2.5.1 will be extracted from <Diffs> and adjusted p-values will be calculated using following code:

PROC multtest inpvalues= <rawPvalues> hoc; Run;

#### 5.2.2 Supplementary Analysis

The multiple imputation for the Supplementary estimand will be done using the "five macros", which fit a Bayesian Normal RM model and then impute post withdrawal data under a series of possible post-withdrawal profiles including J2R, CIR and CR as described by Carpenter et al (Carpenter et al. 2013).

In "five macro", all intermediate missing values will be imputed assuming MAR and the MNAR part of the model is restricted to patterns that are monotone. That means control-based imputations method is only applicable to monotone missing pattern, therefore we need prepare the data in several tweaks in order to use "five macro".

- 0. Prepare the data <in\_data>: <in\_data> stores SANDE score or corneal fluorescein staining score where the structure is one record per FAS subject per day/visit
  - a. For subjects in treatment arms, if a subject experience IEs stated in Section 2.5.4.1, where J2R method is proposed for imputation. Define a new variable <Method\_var> = "J2R" for the subject. Otherwise <Method\_var> = "MAR".
  - b. For subjects in vehicle arm, <Method var> = "MAR"
- 1. Part1A declares the parameter estimation model and checks consistency with the dataset

```
%part1A(Jobname=ECF, Data=<in_data>, Subject=USUBJID, Response=<Chg>, Time=<
Visit>, Treat=<Treatment>, Covbytime=<Baseline>);
```

2. Part1B fits the parameter estimation model using the MCMC procedure and draws a pseudoindependent sample from the joint posterior distribution for the linear predictor parameters and the covariance parameters.

```
%part1B(Jobname=ECF, Ndraws=1000, thin=250, seed=20210301);
```

3. Part2A calculates the predicted mean under MAR, and under MNAR for each subject based on their withdrawal pattern once for each draw of the linear predictor parameter estimates. The choice of MNAR is controlled by the method used, which may vary from subject to subject.

```
%part2A(Jobname=ECF,methodV=<Method var>,refV=<Ref var>);
```

<Ref var> is the variable indicating the reference group for all subjects in the study

4. Part2B imputes the intermediate missing values using MAR and the trailing missing values using MNAR, by deriving the conditional distribution for the missing values conditional on the observed values and covariates, using the appropriate sampled covariance parameter estimates.

```
%part2B(Jobname=ECF, seed=20210302);
```

5. Instead of running Part3 from 'five macros', we will carry out MMRM analysis as stated in Section 5.2.1 per imputation for <Dataset>. It then combines the least-squares means, their differences and p-values using the MIANALYZE procedure to provide final results.

P-values from three comparisons requested in Section 2.5.1 in PROC MIANALYZE will be extracted from <Diffs> and adjusted p-values will be calculated using following code:

PROC multtest inpvalues= <rawPvalues> hoc; Run;

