# 2.5 Analysis of the primary objective

The primary aim of the study is to demonstrate improvement in moderate to severe DED with ECF843. This will be evaluated by measuring signs and symptoms as primary estimands.

The symptoms measure of SANDE questionnaire is completed through an electronic diary every evening before bedtime during the study. The signs measure of corneal fluorescein staining will be conducted by the Investigator during site visits based on the Corneal Fluorescein Modified NEI Scale.

For the purpose of the statistical analyses presented in this document, the following terminology is used:

• Jump to Reference (J2R) – the multiple imputation model will be build based on the available vehicle data (including partial information from patients that discontinued prematurely). The imputation model will include important background characteristics and observed data.

• Missing at Random (MAR) – the multiple imputation model will be build based on similar patients (i.e. with the same covariates and observed measurement history) in the same treatment arm.

• Retrieved drop-out (RDO) patients - Patients who discontinue study treatment and decide to remain in the study by following an abbreviated schedule of assessments.

• Intercurrent events (IE) - Events that occur after treatment initiation and either preclude observation of the variable or affect its interpretation (e.g., rescue medications, discontinuation of treatment, switching treatment, terminal events such as death, etc.)

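### The multiple-imputation model in SAP 5.2.2 leaves out Sjögren's status, which the analysis model fitted to each imputed dataset contains

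*SAP*

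**What the plan says.** SAP 5.2.2 gives the macro calls for the multiple imputation. Its first step has this role: "Part1A declares the parameter estimation model and checks consistency with the dataset". The end of that call reads "Visit>, Treat=<Treatment>, Covbytime=<Baseline>", so that its one covariate argument is "Covbytime=<Baseline>", and the call then closes. The next step fixes the number of draws, the thinning and a seed. The third, "part2A(Jobname=ECF,methodV=<Method var>,refV=<Ref var>", adds a method variable and a reference variable but no covariate, and the fourth adds only a second seed. No step names Sjögren's status.

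The analysis model is in SAP 5.2.1, introduced by "The following MMRM model will be used for the primay estimand and supplementary estimand". For SANDE it begins "change from baseline in SANDE = intercept + baseline SANDE + treatment + day + Sjogren's Syndrome (yes/no", and the corneal staining model has the same structure. The last step of SAP 5.2.2 fits this MMRM to each imputed dataset and combines the results.

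Three other places bear on the point:

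- SAP 2.5 says of jump-to-reference: "The imputation model will include important background characteristics and observed data". For missing-at-random imputation it refers to subjects in the same arm who match on covariates and measurement history.
- Protocol 6.3.2 makes Sjögren's Syndrome the only stratification factor.
- SAP 5.5 takes the actual stratum for every analysis when the recorded diagnosis and the randomization system disagree.

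**The concern.** An imputation model should contain at least the covariates of the model that will analyse the completed data. Here the imputed values assume that, given treatment, baseline and the subject's observed scores, Sjögren's status carries no further information. The MMRM then estimates a Sjögren's effect from data that partly assume there is none. That pulls the stratum coefficient towards zero. It can also shift the treatment difference if dropout depends on Sjögren's status in one arm but not in the other.

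At stake is the accuracy of the supplementary treatment-policy estimate. Both documents state that sensitivity analysis is not applicable (Protocol 12.4.5, SAP 2.5.4.2), so this is the planned analysis that treats intercurrent events and dropout differently from the primary one.

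**Working it through.** **1. Terms named in the two models**

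| Term | Imputation model (SAP 5.2.2) | MMRM on each imputed dataset (SAP 5.2.1) |
|---|---|---|
| Treatment | yes | yes |
| Day or visit | yes | yes |
| Baseline by day or visit | yes | yes |
| Sjögren's status | no | yes |

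Sjögren's status is the only covariate of the analysis model missing from the imputation call. The call is complete and shows no redaction gap.

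**2. The plan's own scale (Protocol 12.8.1)**

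The inputs are 112 per arm, difference 10 mm, SD 23 mm and two-sided alpha 0.05/3. The standard error is 23 × √(2/112) = 3.07 mm. Power is 80.5% by normal approximation and 79.9% by noncentral t, so the stated 80% is reproduced. The point does not depend on this figure; it only sets the scale.

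**3. Treatment difference: formula under assumed inputs**

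Let p be the Sjögren's prevalence and g its effect on SANDE change. Let m1 and m0 be active-arm dropout in subjects with and without Sjögren's, with vehicle dropout equal across strata. Under jump-to-reference without the stratum, every missing active subject receives the vehicle profile mean, gp.

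- Missing Sjögren's subjects: share p·m1, error gp − g = −g(1−p).
- Other missing subjects: share (1−p)·m0, error +gp.
- Sum: −g·p·(1−p)·(m1 − m0).

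With g = 10 mm, m1 = 30% and m0 = 10%:

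- p = 20%: 10 × 0.20 × 0.80 × 0.20 = 0.32 mm
- p = 10%: 10 × 0.10 × 0.90 × 0.20 = 0.18 mm
- p = 5%: 10 × 0.05 × 0.95 × 0.20 = 0.095 mm

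These figures ignore the subject's own earlier scores. If one earlier score is used, at an assumed correlation of 0.5, about half of the error is recovered: 0.32 × 0.5 = 0.16 mm, 0.09 mm and 0.05 mm. With equal dropout by stratum the shift is zero.

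**4. Simulation under assumed inputs**

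One pair of arms of 112, two visits, correlation 0.5, SD 23 mm, treatment effect 10 mm, stratum effect 10 mm, jump-to-reference in the active arm, the same dropout pattern in both arms, 1,500 runs per cell. Entries are means in mm, with and then without the stratum in the imputation model.

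| Prevalence | Dropout, Sjögren's / other | Treatment difference | Sjögren's coefficient | Fall in coefficient |
|---|---|---|---|---|
| 5% | 10% / 10% | 8.92, 9.06 | 10.15, 9.46 | 0.69 |
| 5% | 30% / 10% | 8.94, 8.90 | 9.05, 7.33 | 1.72 |
| 10% | 10% / 10% | 8.98, 9.17 | 9.91, 9.49 | 0.42 |
| 10% | 30% / 10% | 8.95, 8.85 | 8.71, 7.38 | 1.33 |
| 20% | 10% / 10% | 8.99, 9.21 | 10.01, 9.48 | 0.53 |
| 20% | 30% / 10% | 8.71, 8.60 | 8.95, 7.63 | 1.32 |

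*Treatment difference.* It shifts by 0.04 to 0.22 mm. The Monte Carlo standard error of a shift is about 3.07 × √(2/1500) = 0.11 mm, so the largest is about two standard errors. When both arms drop out alike, the errors in step 3 cancel between arms, so these shifts are best read as noise. The case that does move the contrast is stratum-dependent dropout in one arm only (step 3).

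*Sjögren's coefficient.* The expected fall is about (1 − 0.5)·g·[m1(1−p) + m0·p]. With equal dropout this is 0.5 × 10 × 0.10 = 0.50 mm. With 30% versus 10% it is 1.45, 1.40 and 1.30 mm for p = 5%, 10% and 20%. The simulated falls agree apart from noise. As a share of the assumed 10 mm they run from 0.42/10 = 4% to 1.72/10 = 17%.

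**The case against.** The strongest reply has five parts.

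- **The code is not final.** SAP 5.2.1 defers full code, including the imputation, to the TFL shells, which are not among the documents. What will be run cannot be seen. But SAP 5.2.2 writes the call out with fixed draws and seeds, so the mismatch stands in the SAP as written.
- **SAP 2.5 never names Sjögren's for imputation.** This stands. The wording there is general, and a reader who infers that the SAP promised this covariate and then broke the promise goes further than the text. The firm mismatch is between SAP 5.2.2 and SAP 5.2.1.
- **Observed data carry much of the information.** Largely right. The draws condition on observed values, SANDE is recorded daily, and data retrieved after treatment discontinuation are used where they exist. Only what is still missing is imputed. This reduces the effect without removing it.
- **The stratum coefficient is not an estimand.** Correct: no objective or hypothesis concerns it. The part that matters for inference is the shift in the treatment difference, and that is small.
- **The numbers rest on assumptions.** Correct. The documents give no Sjögren's prevalence, prognostic effect or dropout by stratum, and the illustration covers SANDE only, not corneal staining.

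**Conclusion.** The point holds as a minor misalignment. The imputation model is smaller than the analysis model by one term, and that term is the randomization stratum. If imputation uses the subject's earlier scores, the treatment difference moves by about 0.2 mm or less against a planned 10 mm; the crude formula that ignores those scores reaches 0.32 mm at its most unfavourable setting. The stratum coefficient is attenuated by roughly 4-17%. All of these sizes depend on the assumed prevalence of 5-20%, stratum effect of 10 mm, dropout of 10% or 30%, and within-subject correlation of 0.5.

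Two wider readings are tempting but unsupported. One is that the primary result or the Sjögren's subgroup result is biased. The primary MMRM contains the stratum and uses no multiple imputation, and SAP 2.5.4 runs the subgroup analyses with the primary model and strategy. The other is that the supplementary analysis is the only check on the primary result. SAP 2.5.4 also plans subgroup analyses and summary statistics by visit, and the supplementary analysis targets a different estimand.

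**What to change.** In the `%part1A` step of SAP 5.2.2, add Sjögren's status as a categorical main-effect covariate for both endpoints. Use the same variable as the MMRM, that is, the actual stratum under SAP 5.5. Keep it a main effect, as in SAP 5.2.1: a stratum-by-day term over daily SANDE scores would add many parameters in what may be a small stratum. Carry the change into the TFL shells. It would also help to list the imputation covariates by name in SAP 2.5. If the sponsor prefers to leave the stratum out, the SAP should say why.

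The cost is one covariate in the macro call and a line of text, made before database lock. Sample size, alpha, stated power and the primary analysis do not change.

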# 5.3 Rule of exclusion criteria of analysis sets

The following table provides the definitions of the protocol deviations of the study, together with the exclusion rules.

 PD ID
 Deviation Text
 Data exclusion

 INCL01
 written informed consent not obtained
 Exclude from all analysis sets

Table 5-1Protocol deviations

Novartis SAP

PD ID	Deviation Text	Data exclusion
INCL02	Patient < 18 years of age at Screening	Include in all analysis sets
INCL03	patient not able or willing to follow protocol or assessments	Include in all analysis sets
INCL04	< 6 months dry eye diagnosis in both eyes	Include in all analysis sets
INCL05	not use or need AT, gels or lubricants	Include in all analysis sets
INCL06	Tear Break-up Time (TBUT) > 5 seconds in both eyes	Include in all analysis sets
INCL07	Composite corneal fluorescein staining score < 4 (modified NEI scale) in both eyes	Include in all analysis sets
INCL08	In office SANDE global ocular discomfort score < 60mm	Include in all analysis sets
INCL09	Eye Dryness Score < 40mm	Include in all analysis sets
INCL10	Schirmer score 0 or > 10 mm after 5 min both eyes	Include in all analysis sets
INCL11	Sjogrens Syndrome patient lacks confirmed diagnosis	Include in all analysis sets
EXCL01	Ocular infection (bacterial, viral, or fungal) in either eye within 30 days prior to Screening	Include in all analysis sets
EXCL02	Use of artificial tears, gels, lubricants within 4 hrs of conducting assessments at Screening	Include in all analysis sets
EXCL03	contact lens use in either eye within 14 days of Screening, and any use during study	Include in all analysis sets
EXCL04	uncontrolled ocular rosacea, posterior blepharitis, or MGD	Include in all analysis sets
EXCL05	Clinically significant conjunctivochalasis in either eye	Include in all analysis sets
EXCL06	Corneal conditions, dystrophies, scar, pterygia, keratoconus in either eye	Include in all analysis sets
EXCL07	history ocular HSV or infection, GvHD, Stephen's Johnson Syndrome, sarcoidosis	Include in all analysis sets
EXCL08	active or history of ocular allergies during time patient will be in study	Include in all analysis sets
EXCL09	hypersensitivity to ECF843, stains, Xiidra, or other	Include in all analysis sets

Novartis SAP

PD ID	Deviation Text	Data exclusion
EXCL10	current punctal plugs or punctal cauterization or occlusion	Include in all analysis sets
EXCL11	unstable chronic meds 30 days prior to Screen	Include in all analysis sets
EXCL12	Use of Restasis, Cequa, or Xiidra within 30 days prior to Screening	Include in all analysis sets
EXCL13	Medical device use to treat MGD within 3 months prior to Screen	Include in all analysis sets
EXCL14	Use of ocular, nasal, inhaled, or systemic corticosteroids within 30 days of Screen or during the study	Include in all analysis sets
EXCL15	history of corneal refractive surgery	Include in all analysis sets
EXCL16	any intraocular surgery including cataract surgery within 6 months prior to Screening	Include in all analysis sets
EXCL17	Chronic systemic disease diagnosed within the last 30 days or not stable 30 days prior to Screen	Include in all analysis sets
EXCL18	Use of other investigational drugs within 5 half-lives of enrollment, 30 days, or return to baseline	Include in all analysis sets
EXCL19	History of malignancy of any organ system treated or untreated within 5 yrs	Include in all analysis sets
EXCL20	any systemic or ophthalmic condition that precludes study participation per Investigator opinion	Include in all analysis sets
EXCL21	Pregnant or nursing (lactating) women	Include in all analysis sets
EXCL22	women of child bearing potential unless using basic methods of contraception during study	Include in all analysis sets
WITH01	Subject withdrew consent but continued to receive study medication	Include in all analysis sets
TRT01	randomized subject administered incorrect treatment and/or dose	Include in all analysis sets

Novartis SAP

PD ID	Deviation Text	Data exclusion
TRT02	Investigational or other study treatment dose adjustments and/or interruptions made	Include in all analysis sets
COMD01	Prohibited concomitant medication and/or procedure as per protocol	Include in all analysis sets
COMD02	Prohibited concomitant medication change as per protocol	Include in all analysis sets
OTH01	Any other protocol deviation with impact on patient rights or safety	Include in all analysis sets
OTH02	Any other protocol deviation with impact on trial's scientific value/data integrity	Include in all analysis sets
OTH03	Any other PD without impact on patient safety/rights or trials's scientific value/data integrity	Include in all analysis sets
OTH04	Subject missed a visit or assessment not allowed in the study	Include in all analysis sets
OTH05	Missed visit due to COVID-19	Include in all analysis sets
OTH06	Visit not done at study site due to COVID-19	Include in all analysis sets
OTH07	Assessment / procedure changed due to COVID-19	Include in all analysis sets
TRT03	Drug supply method changed due to COVID-19	Include in all analysis sets
TRT04	Treatment not given due to COVID-19	Include in all analysis sets
OTH08	Discontinuation due to COVID- 19	Include in all analysis sets
OTH09	Unblinding for non-emergent situation	Include in all analysis sets
OTH10	staining strips moistened with anesthetic	Include in all analysis sets
TRT05	patient noncompliance with study drug	Include in all analysis sets
OTH11	SANDE compliance <50%	Include in all analysis sets

# 5.4 Exclusion of subjects with data issue of conjunctival lissamine staining from analysis

Site used a conjunctival lissamine green grading scale different from the Oxford scale in the protocol. The reported scores could not be adjusted or correlated retrospectively.

The impacted subjects

will be

flagged in listings but excluded in the summary for conjunctival lissamine staining.

